	
 Raw values and change from the Inclusion Visit in CAJIS total score at each Follow-up Visit; Raw values and shift from the Inclusion Visit in the use of assistive devices and adaptations for daily living at each Follow-up Visit; Raw values and change from the Inclusion Visit in % of worst score for total score, upper extremities subscore and mobility subscore using the adult form of the FOP-PFQ for all participants, at each Follow-up Visit; Type and frequency of healthcare utilization Raw values and change from the Inclusion Visit in observed and % predicted FVC at each Follow-up Visit; Raw values and change from the Inclusion Visit in observed and % predicted FEV₁ at each Follow-up Visit; Raw values and change from the Inclusion Visit in absolute and predicted FEV₁/FVC ratio at each Follow-up Visit; Raw values and change from the Inclusion Visit in observed and % predicted DLCO at each Follow-up Visit; Raw values and change from the Inclusion Visit in physical and mental function (mean global physical and mental health score converted into T-scores), using the adult form of the PROMIS Global Health Scale for all participants, at each Follow-up Visit;

To describe the number of investigator-reported flare-ups, flare-up outcomes (extra bone growth, restricted movement) and flare-up duration by body location and overall;	
Raw values and change from the Inclusion Visit in number of investigator-reported flare-ups, flare-up outcomes (extra bone growth, restricted movement) and flare-up duration at each Follow-up Visit by body location and overall;Percentage of participants with extra bone growth associated or not with a flare-up at each Follow-up Visit;

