9.4.3.7 Flare-ups

Actual values as well as the change from the Inclusion Visit in number of investigator-reported flare-ups, flare-up outcomes (extra bone growth, restricted movement) and flare-up duration will be presented for each visit by body location and overall.

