## 2.6 Change from Statistical Section of the Protocol

As per section 9.4.1 of the protocol it stated that all analyses will be performed by parent study (PVO-1A-301 or PVO-1A-202/PVO-1A-204), by palovarotene status at the time of transition to Study CLIN-60120-452 (treated, not treated) and treatment regimen (chronic treatment only, flare-up treatment only, chronic & flare-up treatment) and overall.

However, all analyses will only be performed overall and by treatment regimen (chronic treatment only, flare-up treatment only, chronic & flare-up treatment).

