#### 5.7.3.7 Flare-ups

The number of flare-ups since the last visit (for post-inclusion visits) as well as the number of participants with investigator-reported flare-ups, number of intercurrent flare-ups, location of flare-ups, flare-up causes, flare-up symptoms, flare-up outcomes (restricted movement and bone formation) and flare-up duration will be presented for each scheduled visit by body location and overall with descriptive statistics. For the summary of flare-ups, percentages will be calculated using the number of participants with at least a flare-up at each visit as the denominator. The following body locations will be presented:

- Shoulder (Includes left and right shoulder)
- Elbow (Includes left and right shoulder)
- Wrist or Hand (Includes left wrist or hand and right wrist or hand)
- Hip (Includes left hip and right hip)
- Knee (Includes left hips and right hip)
- Ankle or Foot (Includes left ankle or foot and right ankle or foot)
- Back (Includes upper back and lower back)
- Chest
- Abdomen
- Head and Anterior neck
- Jaw and Submandibular Area
- Spine (Includes Cervical Spine, Thoracic Spine and Lumbar Spine)
- Other (Includes all other locations)

The number of flare-ups since the last visit will be calculated by totalling the number of distinct flare-ups (based upon the flare-up start dates, not including intercurrent flare-ups) using the visit windows as defined in section 6.1.

Duration of flare-up will be defined as (date of end of flare-up – date of start of flare-up + 1) and will be calculated for each distinct flare-up before summing across each participant.

An intercurrent flare-up is defined as a new flare-up or marked worsening of the original flare-up at any time during a flare-up based treatment cycle.

In addition, the total number of flare-ups across the study, the duration of study participation, the individual flare-up rate per month and the global flare-up rate (including the 95% confidence interval derived using a poisson model offset by the duration of study participation) across all participants per month will be summarised.

The individual flare-up rate per month will be defined as  $[(\text{Number of flare-ups during study follow-up}) / \text{duration in the study (in months)}]$ . This duration will be calculated as  $(\text{end of study date} - \text{informed consent date} + 1) / 30.4375$ .

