The global flare-up rate will be calculated as the sum of flare-ups across all participants / sum of durations in the study(months).

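### SAP 5.7.3.7: the per-visit flare-up count leaves out new flare-ups that arise during a treatment cycle, the rates do not say whether they do the same, and the rate CI is plain Poisson

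*SAP*

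**What the plan says.** The protocol's secondary endpoint (section 3, Table 3) is "Raw values and change from the Inclusion Visit in number of investigator-reported flare-ups", by body location and overall. Protocol 9.4.3.7 plans to present "Actual values as well as the change from the Inclusion Visit in number of investigator-reported flare-ups". Neither place excludes any class of flare-up.

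SAP 5.7.3.7 obtains the number since the last visit by totalling distinct flare-ups within visit windows, "based upon the flare-up start dates, not including intercurrent flare-ups". It defines an intercurrent flare-up as "a new flare-up or marked worsening of the original flare-up at any time during a flare-up based treatment cycle". Protocol 4.3 and Table 4 explain the same term as a new location or a marked worsening of the original flare-up. The number of intercurrent flare-ups is a separate item in the same SAP table, per visit, by location and overall.

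Three further summaries follow in SAP 5.7.3.7:
- a study total;
- an individual monthly rate with numerator "Number of flare-ups during study follow-up";
- a global rate: "The global flare-up rate will be calculated as the sum of flare-ups across all participants", divided by summed durations.

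None of the three mentions intercurrent flare-ups. The global rate's 95% CI is "derived using a poisson model offset by the duration of study participation".

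SAP 2.6, which records changes from the protocol's statistical section, lists only the analysis groupings: "However, all analyses will only be performed overall and by treatment regimen".

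**The concern.** Leaving out worsening of an existing flare-up avoids counting one event twice. Leaving out a flare-up at a new site does not, because that is a new event and belongs in the endpoint. The SAP's definition puts both under one label, and the exclusion removes both.

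The silence on the rates is a separate gap. Two programmers could follow the SAP faithfully and report different rates. If the exclusion applies, the rates are low, because the days spent in a cycle stay in the denominator while new flare-ups on those days leave the numerator. If it does not apply, the study total will not agree with the sum of the per-visit counts.

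The interval is a third matter. A Poisson model with an offset assumes that, given follow-up time, every participant has the same flare-up rate. If rates differ and all flare-ups are counted, the interval is too narrow. In a study without hypothesis tests, estimates and intervals are the reported result.

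**Working it through.** **No figure to reproduce.** The documents state no expected flare-up rate, no dispersion and no share of in-cycle events at a new location. Those inputs are assumed below. From the documents come the 84-day cycle and its restart on an intercurrent flare-up (Protocol 4.3, Table 4; SAP 2.2), the maximum of 87 participants (SAP 2.3) and the three-year maximum duration (SAP 2.2).

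**Undercount in the per-visit number.** Let r be the rate of reported events per year, τ = 84/365.25 = 0.230 years, and f the share of in-cycle events that are at a new location. Each counted flare-up opens a cycle in which nothing further is counted.
- Counted rate without restart: c = r/(1 + rτ). With restart: c = r·exp(−rτ).
- Share of new flare-ups left out: f(r − c) / [c + f(r − c)].

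At r = 1 without restart, c = 1/1.230 = 0.813 and r − c = 0.187. With restart, c = 0.795 and r − c = 0.205.

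| New-location share f | No restart | Restart |
|---|---|---|
| 25% | 0.047/0.860 = 5% | 0.051/0.846 = 6% |
| 50% | 0.093/0.907 = 10% | 0.103/0.897 = 11% |
| 100% | 0.187/1.000 = 19% | 0.205/1.000 = 21% |

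Over the same shares, the range is 3% to 11% at 0.5 per year and 10% to 37% at 2 per year. Differences between participants raise the figure, since frequent flarers spend more time in cycles. At a mean of 1 per year, f = 50% and gamma-distributed individual rates with shape 2, 1 and 0.5, it is 14%, 17% and 21% (16%, 20% and 28% with restarts).

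**Effect on the rate.** At r = 1, f = 50% and no restart, new flare-ups occur at 0.907/12 = 0.076 per month. A rate that applies the exclusion targets 0.813/12 = 0.068. The SAP text permits either.

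**Coverage of the Poisson interval, all flare-ups counted.** Assume 87 participants, follow-up T uniform on 0.5 to 3 years, a mean of 1 flare-up per year, and individual rates that are gamma with shape k. The variance of the total, relative to Poisson, is φ = 1 + r·E(T²)/(k·E(T)).
- E(T) = 1.75 and E(T²) = 1.75² + 2.5²/12 = 3.583, so φ = 1 + 2.048/k.
- Approximate coverage is 2Φ(1.96/√φ) − 1.

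| k | φ | Formula | Simulated Poisson |
|---|---|---|---|
| no heterogeneity | 1.00 | 95% | 95% |
| 2 | 2.02 | 83% | 84% |
| 1 | 3.05 | 74% | 74% |
| 0.5 | 5.10 | 61% | 62–63% |

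A participant-level sandwich variance gave 93% to 95% in all four rows.

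**Coverage if the exclusion applies to the rate.** The interval is judged against the true rate of the events counted. Poisson coverage is then 98% without heterogeneity and 94–95%, 90–92% and 84–89% at shape 2, 1 and 0.5. Blocking events within a cycle reduces the variance, so undercoverage is milder.

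**Small columns.** Results are also shown by regimen, where groups may be small. With normal quantiles the sandwich interval covers only 87–92% at n = 10 and 85–89% at n = 5. Using t quantiles with n − 1 degrees of freedom gives 92–97%.

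**The case against.** The case on the other side has real force.

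- **Nothing disappears.** Intercurrent flare-ups have their own row per visit and by location, and SAP 5.7.3 lists all secondary endpoints. A reader can add the two rows to recover all reported events. This stands, and it limits the point. The tables still cannot separate new-location events from worsening, so the number of new flare-ups cannot be read from them.
- **It may be operational detail rather than a departure.** Protocol section 9 leaves technical detail to the SAP, and the protocol gives no counting rule for events within a cycle. Absence from SAP 2.6 is therefore weak evidence of an undeclared change. The mismatch between count and endpoint does not depend on it.
- **The sizes are assumed.** True for every one of them. The wording gaps in the count and in the rates need no assumption.
- **The CI point is conditional.** Also true: without heterogeneity the Poisson interval is adequate, and the analysis is descriptive.

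Two stronger readings are tempting. First, a cycle may start after a traumatic event with no flare-up, so a reader might infer that the first flare-up in it is always counted as zero. The documents leave this unsettled: the SAP definition could be read that way, but the protocol's definition presupposes an original flare-up. Second, Protocol 4.3 cites a patient survey in which two-thirds of falls induced a flare-up, and a reader might take that as the size of the undercount. It gives neither the share of cycles started by trauma nor the timing of the flare-up relative to the cycle, so it cannot serve as a magnitude.

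**Conclusion.** The concern holds in three parts. As written, the per-visit number is below the number of investigator-reported flare-ups whenever an intercurrent one is reported, and below the number of new flare-ups whenever one of these is at a new location. The study total and both rates lack a defined numerator. The global-rate CI is too narrow if participants differ in flare-up rate and all flare-ups are counted.

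The first two parts rest on the text alone. Their size is illustrative: 5% to 21% at an assumed one event per year with equal rates across participants. The third rests on heterogeneity that the documents neither state nor rule out. The low coverage figures and the low rates should not be read together: the lowest coverage arises when all flare-ups are counted, the low rates when they are not.

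This merits an SAP correction before database lock. It concerns a descriptive secondary endpoint and affects no test or decision rule.

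**What to change.** In SAP 5.7.3.7:

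- **(a) Numerator.** Count new-location flare-ups arising during a cycle in the per-visit number, the study total and both rates, and state that one numerator serves all of them. Report worsening-only intercurrent events separately. State that the first flare-up in a trauma-started cycle counts as new. Protocol 8.1.7 collects a location for each flare-up but does not say that every intercurrent event has its own record, so check this before database lock. If the records cannot be split by location, show the total and the rates with and without intercurrent events.
- **(b) Interval.** Keep the global rate as the ratio of sums. Take its 95% CI from a participant-level robust (sandwich) variance, with a small-sample correction such as t quantiles with n − 1 degrees of freedom for the by-regimen columns. Interpret very small columns with caution.

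The Elbow and Knee location labels name shoulders and hips; correcting them is clerical.

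The cost is a few sentences of SAP text and a few lines of code. The downside is higher counts and usually a wider interval: with 87 participants and a 50% new-location share, about 0.9 times the Poisson width without heterogeneity and up to 1.8 times at gamma shape 0.5, before the t correction.

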- Technology adaptions (adapted keyboard, voice activated computer software, wireless keyboard and mouse, trackball, adapted stand for computer use, typing stick, onscreen keyboard that is not normally part of the device);
- Sports and recreation adaptions (protective helmet/body gear, adapted bicycle, other adapted recreational gear);
- School adaptions (adapted desk, adapted chair, reaching tools, special electronics for learning, adapted curriculum);
- Medical therapies for daily living (supplemental oxygen, physical therapy, hydrotherapy, energy medicine therapy, occupational therapy, lymphoedema massage treatments and wraps, wound care specialist, positive expiratory pressure mask or spirometer for breathing exercises).

8.1.5 *Healthcare Utilisation*

The healthcare utilisation information that will be collected does not rely on specific validated questionnaires, but on tailored questions which will assess the type and frequency of health services used in the past 6 months/since the last visit.

8.1.6 *Lung Function Assessments*

Lung function will be assessed at the Inclusion Visit, Follow-up Visits and at the EOS/EW Visit.

The lung function parameters of observed FVC (litres) and % predicted FVC, observed FEV₁ (litres) and % predicted FEV₁ and the absolute and predicted FEV₁/FVC ratio are obtained by spirometry.

The parameters of observed (traditional unit of mL/min/mmHg or International System of Units (SI unit) of mmol/min/kPa) ([Graham et al., 2017](#)) and % predicted DLCO is obtained by the DLCO test. This provides information on the efficiency of gas transfer from alveolar air into the bloodstream. Carbon monoxide has a high affinity for haemoglobin, and it follows the same pathway as that of oxygen to finally bind with haemoglobin. Inhaled carbon monoxide is used for this test due to its high affinity for haemoglobin which is 200-250 times that of oxygen ([Modi and Cascella, 2020](#)).

8.1.7 *Flare-up Assessment*

For each flare-up, the location of the flare-up, flare-up cause, flare-up start and stop date, whether it is ongoing, flare-up concomitant medication, symptoms and outcome (resulted in extra bone growth, restricted movement) will be collected at the Inclusion Visit (for ongoing flare-up, data from parent EOS Visit will be entered again in the Study CLIN-60120-452 eCRF), the Follow-up Visits and the EOS/EW Visits.

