### 5.1.4 *Reference Start Date and Study Day*

Reference start date is defined as the day of the first IMP administration of palovarotene (Day 1) in Study CLIN-60120-452. Study day will be calculated as:

- The difference between the event date and the reference date plus one day, if the event is on or after the reference date.
- The difference between the event date and the reference date, if the date of event is prior to the reference date.

Study day will appear in any listings where an assessment date or event date appears.

In case of partial or missing event date, study day will appear missing while any associated durations will be presented based on the imputations described in appendix A3.

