#### 5.7.1.2 Handling of Dropouts and missing data

Diligent attempts will be made to limit the amount of missing data and to follow-up all enrolled participants to collect the primary and secondary efficacy endpoints for the statistical analysis.

With the exception of the QoL questionnaires, where missing data will be handled based upon the calculation of the derived scores, missing data will not be replaced but will be displayed in all relevant tables.

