### 5.8.2.2 Duration of Flare-up Treatment

For participants receiving flare-up treatment, duration of flare-up treatment (days) is defined as total flare-up cycle dosing periods (days) across all flare-up cycles. This includes any days for which the participant is receiving persistent flare-up symptom or intercurrent flare-up treatment.

For a flare-up cycle, the flare-up cycle dosing period (days) is defined as days that participants received flare-up-based treatment and is calculated as (last dose date of the flare-up cycle – first date of the flare-up cycle – days where flare-up medications were not taken/interrupted during the flare-up cycle + 1).

The mean duration of flare up treatment is defined as the total duration of flare-up treatment (across all cycles) divided by the number of flare-up treatment cycles for each individual.

The duration of persistent flare-up symptom and intercurrent flare-up treatment will be calculated in a similar manner.

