### A3.Partial/Missing Date Convention

In all listings, missing or incomplete dates should be left as they have been recorded. However, for calculation / sorting / assignation based on dates, the following methods will be used:

- The most conservative approach will be systematically considered (i.e. if the onset date of an AE/concomitant medication is missing / partial, it is assumed to have occurred during the study treatment phase (i.e. a TEAE for AEs) except if the partial onset date or the stop date indicates differently).
- Where this is possible, the derivations based on a partial date will be presented as superior inequalities (i.e.: for an AE started in FEB2004 after the first IMP administration performed on 31JAN2004, the days since last dose will be “ $\geq 2$ ”, similarly the duration of ongoing AEs or medication will be “ $\geq xx$ ” according to the start and last visit dates).

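### Flare-up duration is summed within participant, so it mixes number with length, and the SAP does not say how flare-ups without a stop date enter the summary

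*SAP*

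**What the plan says.** Protocol Table 3 lists flare-up duration among the secondary endpoints. Protocol 9.4.3.7 says that "flare-up duration will be presented for each visit by body location and overall"; it does not mention a sum. For each flare-up, Protocol 8.1.7 collects "flare-up start and stop date, whether it is ongoing", so records without a stop date are expected.

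SAP 5.7.3.7 takes end date minus start date plus 1 and adds that this "will be calculated for each distinct flare-up before summing across each participant". The section defines no mean or median per flare-up and no participant mean. It counts distinct flare-ups by start date within the SAP 6.1 visit windows and leaves intercurrent flare-ups out of that count.

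Three other SAP rules bear on missing stop dates:
- SAP 5.7.1.2: outside the quality-of-life scores, "missing data will not be replaced but will be displayed in all relevant tables".
- SAP 5.1.4: where an event date is partial or missing, "any associated durations will be presented based on the imputations described in appendix A3".
- Appendix A3: "similarly the duration of ongoing AEs or medication will be" shown as a lower bound (≥ xx) up to the last visit.

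For flare-up treatment, SAP 5.8.2.2 also defines a mean duration: the total is "divided by the number of flare-up treatment cycles for each individual".

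**The concern.** A reader of a table labelled flare-up duration will take it to show how long a flare-up lasts. The summed value answers another question: how many flare-up days a participant accumulated. It goes up when flare-ups are more frequent even if each one is no longer, and it can reverse an ordering. Three 60-day flare-ups score 180, while a single 120-day flare-up scores 120. The flare-up count appears in the same table, but group summaries of a sum and of a count do not give back the distribution of length per flare-up.

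The second issue is the stop date. A flare-up still open when a participant leaves has no value under the formula. Participants leave at different times, because exit follows reimbursement, another access programme or November 2024 (Protocol 4.1). With no stated rule, one programmer could omit the open flare-up and another could close it at last contact. Omission would bias duration downward, because open flare-ups are longer than average. The bias is larger when follow-up is short.

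**Working it through.** The documents give no flare-up duration or rate for this study, so there is no planned figure to reproduce. All lengths below are assumptions for illustration.

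**Step 1. Sum against length per flare-up.**

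| Participant | Flare-ups | SAP value (sum) | Mean per flare-up |
|---|---|---|---|
| A | 1 × 84 days | 84 | 84 |
| B | 3 × 28 days | 84 | 28 |
| C | 3 × 84 days | 252 | 84 |

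A and B get the same value although their flare-ups differ threefold in length. A and C differ threefold although their flare-ups are equally long.

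**Step 2. Mean length if open flare-ups are left out.** Inputs: onset uniform over follow-up T; exponential durations with assumed mean m of 28 or 84 days; T of 365 days, or 1,095 days (the three-year maximum in Protocol 4.1). Write r = T/m.

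- Share open at last contact: p = (1 − e^(−r)) / r.
- Mean of completed flare-ups: {m − (m²/T)[2 − e^(−r)(2 + r)]} / (1 − p).

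For m = 84 and T = 365, r = 4.345 and e^(−r) = 0.01297:
- p = 0.98703 / 4.345 = 22.7%.
- Numerator: 84 − 19.33 × (2 − 0.0823) = 84 − 37.07 = 46.93.
- Completed mean: 46.93 / 0.7728 = 60.7 days, which is 27.7% below 84.

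| Mean m | Follow-up T | Open at last contact | Completed mean | Bias |
|---|---|---|---|---|
| 84 | 365 | 22.7% | 60.7 | −27.7% |
| 84 | 1,095 | 7.7% | 77.0 | −8.3% |
| 28 | 365 | 7.7% | 25.7 | −8.3% |
| 28 | 1,095 | 2.6% | 27.3 | −2.6% |

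The percentage bias depends only on r, so the second and third rows agree.

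**Step 3. Less variable durations.** When r is large, completed mean / m ≈ (1 − E[D²]/(mT)) / (1 − m/T). For a gamma distribution with shape 3, E[D²] = 4m²/3.
- m = 84, T = 365: (1 − 0.307) / (1 − 0.230) = 0.900, a bias of −10%.
- m = 84, T = 1,095: (1 − 0.102) / (1 − 0.077) = 0.972, a bias of −3%.

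**Step 4. Effect on the participant sum.** Steps 2 and 3 concern the mean per flare-up, whereas the SAP reports a sum. A simulation with assumed rates of 1 or 2 flare-ups per year and exponential means of 30, 60 or 120 days compared full eventual durations with completed flare-ups only. The mean participant sum was lower by 12% to 51% at 1 year and 5% to 22% at 3 years. At 1 year, for example, 47.5 falls to 41.7 (−12%) and 278.3 falls to 135.7 (−51%).

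**The case against.** The best defence is that total flare-up days is a legitimate burden measure, that the protocol does not say whether duration means per flare-up or total, and that the study is descriptive with individual values listed. This is fair as far as it goes. The SAP does not contradict the protocol, and no test is affected. But the SAP presents the total under the name duration and gives nothing per flare-up, although for treatment cycles it does divide by the number of cycles.

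Several stronger readings are tempting, and the documents do not support them:
- **A reader might infer that ongoing flare-ups are dropped.** No section says so. SAP 5.1.4 refers missing-date durations to Appendix A3. A3's opening rule is general, although its ongoing-record convention names only adverse events and medication. The defensible statement is that their handling in summaries is unspecified.
- **A reader might infer that the longest flare-ups are the ones lost.** Open flare-ups are longer on average, but one that began just before last contact can be short. In the simulation, among participants with at least two flare-ups and one open, the open one was the longest to date in 19% to 37% of cases at 3 years and 40% to 62% at 1 year.
- **A reader might infer that every flare-up ongoing at a visit is affected.** The analysis follows study completion (SAP 3.3), so a later stop date can still be recorded. Only flare-ups open at last contact matter.
- **A reader might infer that overlapping days are widely counted twice.** SAP 5.7.3.7 leaves intercurrent flare-ups out of the distinct count, which removes much of the overlap.
- **A reader might infer that the value simply grows with time on study.** Presentation by visit window, roughly six months each, limits this.

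It is also fair to object that 84 days is the length of a treatment cycle, which runs even if symptoms resolve earlier, and so does not estimate flare-up length. That is why a range of means is shown.

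**Conclusion.** The summing point holds on the text alone and needs no assumption: the planned output is total flare-up days, which does not describe the secondary endpoint of flare-up duration. The stop-date point holds as a gap in the rules. A lower bound of the form ≥ xx has no stated route into a summary statistic.

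If open flare-ups were omitted, the mean per flare-up would be low by about 8% to 28% with 1 year of follow-up and 3% to 8% with 3 years. This assumes uniform onset and exponential durations with means of 28 to 84 days. Less variable durations shrink it, to about 10% and 3% at the 84-day mean. The direction is firm, but the size depends on inputs that the documents do not give. The primary safety endpoint is not affected. The change should be made because the rule as written misreports a named endpoint and the repair is cheap.

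**What to change.** In SAP 5.7.3.7:
1. Replace the participant sum with duration per distinct flare-up, by body location and overall. Assign each flare-up to the visit window of its start date, which keeps the by-visit presentation and matches the rule already used for the count.
2. Treat flare-ups open at last contact as censored there. Report the Kaplan-Meier median with a 95% CI that allows for repeated flare-ups within a participant, for example from a bootstrap that resamples participants. State the number ongoing.
3. If total flare-up days is kept, label it as such and report it per person-year.

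Start date, stop date and ongoing status are already collected under Protocol 8.1.7, so no new data or procedure is needed. The cost is a revision of the SAP wording and a small amount of extra programming. Intervals will be wide in small location groups, with at most 87 participants in the study.
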